Checkpoint inhibitor treatment is associated with immune-mediated adverse reactions which may affect any organ system. Current data on the incidence of immune-related toxicities are derived from a number of large phase III clinical trials administering weeks to months of continuous checkpoint inhibitor therapy until disease progression, loss of clinical benefit or unacceptable toxicity, in a range of non-prostate tumour types. This study, however, will make use of a **restricted course of treatment limited to 3 infusions 4 weeks apart for metastatic PCa patients and only 1 infusion for low- or intermediate- risk PCa patients**. The incidence and severity of immune-mediated toxicities following a limited course of 3 infusions four weeks apart is not publically available. However, immune-mediated adverse events may occur at any time from the onset of therapy or after completion of treatment and may not be dose-dependent. Most immune-related adverse reactions, however, are low in severity and resolve with appropriate management, though fatal cases have been reported.

The frequency and median time to onset for the major immune mediated toxicities from pooled phase III datasets are shown in Table 1. These data relate to continuous therapy regimes with repeat nivolumab infusions at 2 week intervals. The incidence of toxicities grade 3 or above is <2% for all organ systems. Importantly, more than 50% of immune-mediated toxicities develop after several weeks of continuous treatment, therefore the frequency and risk of treatment-related adverse events following a restricted course of 3 infusions in this study is anticipated to be considerably lower than during licenced clinical use.

Table 1. Immune mediated adverse events after continuous monotherapy with Nivolumab

Immune-mediated toxicity	Frequency (%) *		Median (range) time to onset (months)	Corresponding number of doses at median time of onset **
	Any severity	Grade 3 or above		
Rash	25.6	0.9	1.4 months(0.0-113.7)	3
Diarrhoea / Colitis	12.6	1.3	1.4 months (0.0-20.9)	3
Pneumonitis	3.0	0.8	3.3 months (0.0-19.6)	7
Liver dysfunction/ Hepatitis	6.4	1.8	1.9 months (0.0-10.4)	4
Renal dysfunction	2.7	0.5	2.3 months (0.0-18.2)	5
Endocrinopathy				
Thyroid disorders	8.5	<0.1	2.8 months (0.0-14.0)	6

Adrenal insufficiency	0.4	0.2		
Pituitary disorders	0.4	0.2		

* From pooled dataset n = 2227 (CA209066, CA209037, CA209067 trials) nivolumab 3mg/kg across tumour types

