- Prior to Day 7 study vaccination and checkpoint inhibitor therapy, the subject's diary card entries will be reviewed and any adverse events assessed. Blood tests will be taken as detailed in the schedule of attendances (Appendix 1). The MVA.5T4 vaccine will be administered intramuscularly and the injection site(s) will be covered with a sterile dressing. The participants will remain under observation and vital signs repeated 60 ± 15 min after vaccination when the sterile dressing will be removed and injection site inspected. Participants will then undergo intravenous cannulation and intravenous infusion of nivolumab. The infusion will preferably commence a minimum of 60 minutes following administration of the MVA.5T4 vaccine, but if operationally required simply on the same day as immunisation. Participants will remain in the department for a further 30 ± 15 minutes on completion of the infusion and vital signs repeated prior to departure. At the conclusion of this visit, the intravenous canula will be removed.

Participants will be provided with an alert card, in line with the manufacturer's guidance, outlining the 'red flag' symptoms of immune-mediated checkpoint inhibitor toxicity and emergency contact details for the study medical team. An oral thermometer (if necessary) and new diary card will be given to each participant. In addition to the local and systemic AEs listed above, checkpoint inhibitor associated AEs will also be solicited in the following organ systems:

- Respiratory
- Dermatological
- Gastrointestinal
- Urological

Group 2

Day 0: Enrolment, ChAdOx1.5T4 priming vaccination visit

Subjects will not be considered enrolled in the study until they have received the first study vaccination with ChAdOx1.5T4 on Day 0. Prior to vaccination, blood tests will be taken as detailed in the schedule of attendances (Appendix 1). Following intramuscular administration of the ChAdOx1.5T4 vaccine, the injection site will be covered with a sterile dressing and the patient will stay under observation, in case of immediate adverse events. Observations will be taken 60 ± 15 min after vaccination and the sterile dressing removed and injection site inspected. A diary card, oral thermometer and tape measure will be given to each participant to solicit the following adverse events:

- Localised adverse events
 - o Diameter of redness at vaccination site
 - o Diameter of swelling at vaccination site

- o Pain, warmth and erythema at the vaccination site

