- Systemic adverse events
 - o Recorded temperature and pyrexial episodes
 - o Feverishness
 - o Headaches
 - o Fatigue
 - o Nausea
 - o Generalised muscle aches
 - o Generalised joint aches

Week 4: MVA.5T4 boost vaccination visit and first checkpoint inhibitor therapy

Prior to Week 4 study vaccination and checkpoint inhibitor therapy, the subject's diary card entries will be reviewed and any adverse events assessed. Blood tests will be taken as detailed in the schedule of attendances (Appendix 1). The MVA.5T4 vaccine will be administered intramuscularly and the injection site(s) will be covered with a sterile dressing. The participants will remain under observation and vital signs repeated 60 ± 15 min after vaccination when the sterile dressing will be removed and injection site inspected. Participants will then undergo intravenous cannulation and intravenous infusion of nivolumab. The infusion will preferably commence a minimum of 60 minutes following administration of the MVA.5T4 vaccine, but if operationally required simply on the same day as immunisation. Participants will remain in the department for a further 30 ± 15 minutes on completion of the infusion and vital signs repeated prior to departure. At the conclusion of this visit, the intravenous canula will be removed and participants will be provided with an alert card, in line with the manufacturer's guidance, outlining the 'red flag' symptoms of immune-mediated checkpoint inhibitor toxicity and emergency contact details for the study medical team. In addition to the local and systemic AEs listed above, checkpoint inhibitor associated AEs will also be solicited in the following organ systems:

- Respiratory
- Dermatological
- Gastrointestinal
- Urological

Week 8: Second checkpoint inhibitor therapy

Prior to Week 8, blood tests will be taken as detailed in the schedule of attendances (Appendix 1). The results of clinical haematology and biochemistry (excluding serum PSA and thyroid function tests) taken either on arrival or within the preceding 48 hours will be reviewed prior to proceeding with checkpoint inhibitor therapy. Participants will undergo intravenous cannulation and intravenous infusion of nivolumab following the same administration and monitoring plan as on Week 4.

Week 12: Second cycle of ChAd-MVA immunisation – ChAdOx1.5T4 boost and third checkpoint inhibitor therapy

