Prior to week 12, the subject's diary card entries will be reviewed and any adverse events assessed. Blood tests will be taken as detailed in the schedule of attendances (Appendix 1). The results of clinical haematology and biochemistry (excluding serum PSA and thyroid function tests) taken either on arrival or within the preceding 48 hours will be reviewed prior to administration of vaccine. Then the patients will undergo ChAdOx1.5T4 vaccination and nivolumab infusion, following the same administration and monitoring plan as on Week 4.

Week 16: Second cycle of ChAd-MVA immunisation – MVA.5T4 boost

Prior to week 16, the subject's diary card entries will be reviewed and any adverse events assessed. Blood tests will be taken as detailed in the schedule of attendances (Appendix 1). The results of clinical haematology and biochemistry (excluding serum PSA and thyroid function tests) taken either on arrival or within the preceding 48 hours will be reviewed prior to administration of vaccine. Then the patients will undergo MVA.5T4 vaccination, following the same administration and monitoring plan as on Day 0.

All remaining visits – groups 1 and 2

At all remaining follow up visits, blood tests will be taken as detailed in the schedule of attendances (Appendix 1). Vital signs will be recorded, urinalysis performed, ECOG performance status assessed and if necessary, a medical history and physical examination may be undertaken to determine any relevant interval changes in the participants health. Subjects are recommended to carry their clinical trial alert card, outlining the 'red flag' symptoms of immune-mediated checkpoint inhibitor toxicity and emergency contact details for the study medical team, for a minimum of 6 months after treatment on study.

Telephone communications

Patients will be telephoned by a research nurses on day 2-5 (48-120 hours) following vaccination and/or checkpoint inhibitor therapy to enquire about adverse events and provide further advice regarding completion of the diary card.

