Assessment & recording of adverse events		X	X	X	X	X	X	X	X	X
Radiological assessment (bone scintigraphy, CT scan, MR scan)		X ¹								
Patient alert card provided		X								
Diary card provided		B			C			D		
Diary card returned				X				X		
Haematology ²	2	2		2	2		2	2		2
Biochemistry ²	4	4		4	4		4	4		4
Serum glucose ²	2	2		2	2		2	2		2
Thyroid function tests ²⁻³	2	2						2		
PSA ¹	5	5		5	5		5	5		5
Urinalysis	X	X		X	X		X	X		X
HBsAg, HIV &HCV Ab ¹	5									
Human leukocyte antigen typing (ml)				5						
Exploratory immunology (ml)		30		40			40			40
CTC (ml)		8						8		
ctDNA (ml)		8			8			8		

Total blood volume per visit (ml) ²	20	61		58	21		53	31		53
--	----	----	--	----	----	--	----	----	--	----

* Window is based on preceding IMP administration

¹ Window is -28 days

² Volume can vary by site according to local practices

³ Total triiodothyronine (T3) or free T3c, free thyroxine (T4) and thyroid stimulating hormone (TSH)

Group 2: Participants with Metastatic Prostate Cancer

Table of events (part 2 of 2)

Visit/Telephone Call Number	V7	T4	V8	V9	T5	V10	V11	V12	V13
Time from enrolment (weeks+days)	12	12[contact][contact]
Window (days)*	±7	+3	+3	±2	+3	+3	±7	±14	±14
Informed consent									
Review of inclusion/exclusion criteria	X		(X)	X		(X)	(X)	(X)	(X)
Medical history	(X)		(X)	(X)		(X)	(X)	(X)	(X)
Physical examination (if required)	(X)		(X)	(X)		(X)	(X)	(X)	(X)
Telephone Call		X			X				
Recording vital signs	X		X	X		X	X	X	X
ECOG Status	X			X			X	X	X
ChAdOx1.5T4 vaccination	X								
MVA.5T4 vaccination				X					
Nivolumab infusion	X								
Assessment & recording of adverse events	X	X	X	X	X	X	X	X	X
Radiological assessment (bone scintigraphy, CT MR scan)							X		X
Diary card provided	C			B					
Diary card returned	X			X		X			
Haematology ¹	2		2	2		2	2	2	2
Biochemistry ¹	4		4	4		4	4	4	4
Serum glucose ¹	2		2	2		2	2	2	2
Thyroid function tests ^{1, 2}	2			2			2	2	2
PSA ¹	5		5	5		5	5	5	5
Urinalysis	X		X	X		X	X	X	X
Exploratory immunology (ml)			40			40	30	40	40
CTC (ml)							8		
ctDNA (ml)	8						8		
Total blood volume per visit (ml) ¹	23		53	15		53	61	55	55

Cumulative blood volume = 612m¹

* Window is based on preceding IMP administration

¹ Volume can vary by site according to local practices

² Total triiodothyronine (T3) or free T3c, free thyroxine (T4) and thyroid stimulating hormone (TSH)

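### In Group 2 the week 16 visit returns to the Day 0 adverse-event list, so the second MVA.5T4 dose is followed with a narrower solicited list than the first, 4 weeks after the last nivolumab

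*Protocol*

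**What the plan says.** Group 2 receives nivolumab at weeks 4, 8 and 12 and MVA.5T4 at weeks 4 and 16 (section 4.3).

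- **Day 0 (6.1, Group 2).** "A diary card, oral thermometer and tape measure will be given to each participant to solicit the following adverse events": the list that follows has injection-site reactions and systemic vaccine reactions only.
- **Week 4 (6.1).** Under "Week 4: MVA.5T4 boost vaccination visit and first checkpoint inhibitor therapy", the plan adds to that list: "checkpoint inhibitor associated AEs will also be solicited in the following organ systems", namely respiratory, dermatological, gastrointestinal and urological.
- **Weeks 8 and 12 (6.1).** Both visits, the latter headed "ChAdOx1.5T4 boost and third checkpoint inhibitor therapy", follow the week 4 plan.
- **Week 16 (6.1).** MVA.5T4 is given "following the same administration and monitoring plan as on Day 0".
- **Appendix 1, row "Diary card provided".** Card B at Day 0, C at week 4, D at week 8, C at week 12, B at week 16, and none afterwards.

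Four other sections bear on this. Section 4.6.4 states that "immune-mediated adverse events may occur at any time from the onset of therapy or after completion of treatment" and that participants are monitored continuously for checkpoint-inhibitor toxicity. Section 8.4 has participants record checkpoint-inhibitor symptoms themselves and names no visit at which this stops. Section 8.5 records adverse events of all grades within 28 days of study treatment, and only grade 3 events outside that period. Section 7.1 makes adverse-event incidence, by type and severity, a primary endpoint.

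**The concern.** The safety objective concerns the vaccine given with anti-PD-1. MVA.5T4 is given twice under that combination. After the first dose, participants are prompted for vaccine reactions and for four checkpoint-inhibitor organ systems. After the second, on the natural reading of 6.1 and Appendix 1, they are prompted for vaccine reactions only, although the third nivolumab infusion was 4 weeks earlier and the protocol expects immune-mediated events after treatment ends.

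Prompted and unprompted reporting do not find mild events equally well. The same grade 1 rash or loose stools could be collected by diary in week 15 and depend on spontaneous mention or a general question in week 18, while both fall in the period when all grades are recorded. Pooled incidence by severity would then mix two methods of ascertainment. A lower rate of mild immune-related events after the second MVA.5T4 dose could not be separated from the change of card.

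**Working it through.** **1. Solicitation by visit** (sections 4.3 and 6.1, Appendix 1)

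| Week | Product | Plan in 6.1 | Card | Card returned | Checkpoint-inhibitor events solicited |
|---|---|---|---|---|---|
| 0 | ChAdOx1.5T4 | Day 0 | B | week 2 | no |
| 4 | MVA.5T4 + nivolumab | week 4 | C | week 8 | yes |
| 8 | nivolumab | week 4 | D | week 12 | yes |
| 12 | ChAdOx1.5T4 + nivolumab | week 4 | C | week 16 | yes |
| 16 | MVA.5T4 | Day 0 | B | V10 | no (inferred) |

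Solicitation of the four organ systems is unbroken from week 4 to week 16 and then ends. The last row is inferred from the Day 0 list and the shared card letter.

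**2. Timing**

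- Last nivolumab to the change of card: 16 − 12 = 4 weeks.
- End of all-grade recording after the week 16 dose: 16 + 28/7 = week 20.
- So for about 4 weeks all grades are recordable but the organ-specific prompts are gone.

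**3. The protocol's onset figures (4.6.4, Table 1)**

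Table 1 gives pneumonitis a median onset of 3.3 months, stated as 7 doses at 2-week intervals. Check: 3.3 × (365.25/12)/7 = 14.35 weeks, and 14.35/2 = 7.17, which rounds to 7. The figure reproduces, so the clock runs from the start of nivolumab.

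Counted from the first Group 2 infusion:

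- Pneumonitis: 4 + 14.35 = week 18.35.
- Rash and diarrhoea/colitis (1.4 months = 6.09 weeks): week 10.1.
- Hepatitis (1.9 months = 8.26 weeks): week 12.3.
- Renal dysfunction (2.3 months = 10.00 weeks): week 14.0.

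Week 16 is 84 days, or 84/30.44 = 2.76 months, after the first infusion. With the visits at weeks 8, 12 and 16 at their latest allowed days (+2, +7, +2) it is 95 days, or 3.12 months. Either way it precedes 3.3 months. Among the solicited organ systems, only the pneumonitis median falls after the change.

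**4. Size**

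- Expected pneumonitis at Table 1's 3.0%: 0.03 × 24 = 0.72 cases, of which about half, 0.36, would start after the median.
- One missed case of any event moves a Group 2 rate by 1/24 = 4.2 percentage points.

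Table 1 describes continuous 2-weekly dosing, so it is only an indirect guide to three infusions 4 weeks apart.

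**5. When the week 16 card comes back**

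Appendix 1 has it returned at V10, whose week is not legible in the text available. V4 (week 5) and V6 (week 9) come one week after the preceding dosing visit, which suggests week 17. If it mirrors the first card B, the answer is week 18. The window is +3 days. Exchanging B for C without moving the return date would therefore add only 1 to 2 weeks of prompting and leave 2 to 3 weeks of the all-grade period (20 − 18 = 2; 20 − 17 = 3) without a diary.

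**The case against.** The strongest reply is that the cards follow a consistent logic: B for vaccine alone, C for vaccine with nivolumab, D for nivolumab alone. Each nivolumab card covers about 4 weeks, matching the 28-day rule counted from that infusion. In Group 1 card C runs from week 1 to week 5 on the same pattern. Section 6.1 and Appendix 1 agree on week 16, so this is probably intended and not a slip. That much stands. It does not settle the matter, because the 28-day rule in 8.5 runs from study treatment, which includes the week 16 vaccine, and because sections 4.6.4 and 8.4 describe checkpoint-inhibitor monitoring without such a limit.

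Other ascertainment also continues after week 16: adverse-event assessment at every later visit, a nurse call on days 2 to 5, an alert card carried for at least 6 months, laboratory tests, and oxygen saturation at each visit. This stands too, and it limits the point to mild events. No comparison of rates before and after week 16 is planned.

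Three stronger readings are tempting and are not supported:

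- **That safety monitoring lapses at week 16.** Only the organ-specific diary prompts end.
- **That most pneumonitis would be missed.** An event at week 18.35 is inside the all-grade period and would be recorded if mentioned or found. The onset data come from another regimen, and fewer than one case is expected.
- **That thyroid disorders are affected.** Endocrine events are not among the four solicited systems, and thyroid function is tested at week 16 and at V11 to V13.

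**Conclusion.** The point holds as uneven ascertainment. The second MVA.5T4 dose of the combination has a narrower solicited list than the first, inside the period when all grades are recorded for a co-primary safety endpoint, and this sits poorly with sections 4.6.4 and 8.4. The likely consequence is modest under-counting of low-grade respiratory, skin, gastrointestinal and urological events between week 16 and about week 20. The documents give no figure for how many events prompting would add, so the loss cannot be stated as a number.

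The conclusion assumes that card B carries the Day 0 list, and that the week 16 vaccine counts as study treatment under 8.5. If the printed card B already asks about checkpoint-inhibitor symptoms, only the wording of 6.1 needs correcting. Severity is low; this is a cheap improvement.

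**What to change.** - In section 6.1, week 16, limit the reference to Day 0 to vaccine administration and post-injection observation, and state that the week 4 solicitation list applies.
- In Appendix 1, Group 2, replace card B with card C at V9. Have it completed until the 28-day all-grade period closes (about week 20) and returned at the visit after V10, in place of V10. The later return date is needed; without it the change of card adds little.

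The cost is about 3 more weeks of diary entries (roughly week 17 to week 20) for up to 24 men, using a card that already exists. No dose, visit or treatment rule changes.

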6.2. Additional study procedures

The procedures to be included in each visit are documented in the schedule of attendances in Appendix 1. Additional procedures or laboratory tests may be performed at the discretion of the Investigators, for example in the investigation of potential disease complications or treatment toxicities.

Observations

Vital signs measurements performed on each study visit are, heart rate, blood pressure, oxygen saturations and temperature. Weight and height will additionally be recorded at the screening visit. Vital sign measurements outside the normal range or deviating from the individual's baseline recording will be repeated, clinically evaluated and acted upon as guided by the study nursing and/or medical team.

Sample collection

Blood and urine will be collected for the following laboratory tests and processed at the Oxford University Hospitals NHS Foundation Trust and the Christie Hospital NHS Foundation Trust through an accredited NHS pathology service and disposed of after analysis. The following tests will be undertaken:

- **Haematology:** Full Blood Count and differential
- **Biochemistry:** Sodium, potassium, urea, creatinine, albumin, liver function tests (total bilirubin, ALT, ALP), calcium, magnesium, serum amylase, LDH
- **Serum glucose**
- **PSA blood test**
- **Diagnostic serology:** Hepatitis B surface antigen (HBsAg), Hepatitis C Antibody (HCV Ab), and HIV (HIV Ab).
- **Thyroid Function Tests:** Total triiodothyronine (T3) or free T3c, free thyroxine (T4) and thyroid stimulating hormone (TSH)
- **Clinical immunology:** Human Leukocyte Antigen (HLA) typing
- **Urinalysis** for blood, protein and glucose using dipstick tests

Unprescribed blood tests – at the discretion of the local PI to maintain the welfare of the participant

Prostate tumour tissue will be collected and processed at the Oxford University Hospitals NHS Foundation Trust and the Christie Hospital NHS Foundation Trust, through an accredited NHS pathology service as standard of care. This tissue will be made available for immunohistochemistry performed at the research laboratories (Oxford).

Research blood will be collected for the following assays performed at the research laboratories (Oxford University and University College London) or a central contract laboratory:

- **Exploratory Immunology:** *Ex vivo* ELISPOT assays for interferon gamma; ELISA assays for antibody responses; flow cytometry assays, immunohistochemistry
- **Exploratory Biochemistry:** Four kallikrein peptidases blood test
- **Circulating tumour DNA (ctDNA) and circulating tumour cell (CTC) quantification assays**

Other tests, e.g. immunological assays including ELISPOT assays for other cytokines, T cell epitope mapping, RNA and DNA sequencing or other methods of analysis of genetic polymorphism

potentially relevant to the investigational products may also be performed at the discretion of the investigators.

Multi-parametric Magnetic resonance imaging (mpMRI) – Group 1

Participants in group 1 who are planned to undergo radical prostatectomy will undergo an mpMRI of the prostate and pelvis prior to enrolment on the study as part of standard care in the prostate cancer diagnostic pathway. The subjects who had a pelvic / prostate mpMRI of adequate quality before screening and enrolment will have a repeat on-study mpMRI to evaluate any post-treatment radiographic change in the prostate. The on-study mpMRI should take place prior to radical prostatectomy and a minimum of 7 days after final study checkpoint inhibitor therapy, i.e. on or after study week 4 +7 days. Participants, whose pre-enrolment pelvis/prostate mpMRI is, in the opinion of the reporting radiologist, of low diagnostic value (for example, images are significantly degraded by artefact or post-biopsy haemorrhage), are not required to undergo a repeat on-study mpMRI as the baseline scan will not provide adequate comparator for post-treatment changes. Conventional three-planar MRI including T1 and T2 weighted DCE-MRI and diffusion-weighted sequences will be performed on a 1.5 T magnet. Areas of signal abnormality suspicious for malignancy within the prostate will be graded according to PIRADS criteria. Local T-stage disease identified on scans will be reported as per European consensus on prostate MRI⁴³. The procedure will be performed at the Oxford University Hospitals NHS Foundation Trust and the Christie Hospital NHS Foundation Trust clinical sites.

Tumour Assement by CT scan, bone scintigraphy, MR scan – Group 2

Radiological tumour assessments will be performed at baseline (28 day sceening period), at 6 months and 12 months. The assessments will include a CT scan of chest, abdomen and pelvis and bone imaging, e.g. bone scans or body MRI. CT and MR imaging will be performed with contrast unless this is contraindicated for medical reasons.

The response to treatment in patients with measurable disease will be evaluated per Response Evaluation Criteria In Solid Tumours 1.1 (RECIST 1.1) and per immune-related response criteria (iRECIST).

